### **7.10.1.3 Association between TMB and Efficacy, TMB-evaluable subjects**

The following exploratory analyses of efficacy endpoints will be provided for TMB-evaluable subjects. Treatment effects that will be assessed will be nivo + ipi vs. placebo and nivo vs. placebo. Unless otherwise noted, cutoffs at 10, 11, 13, 14 and 15 mutations/MB will be explored. At each cutoff, TMB Subgroups are defined as follows: TMB high: subjects with TMB  $\geq$  cutoff values, TMB low subjects with TMB  $<$  cutoff value

#### **OS/PFS by TMB**

A summary of OS by TMB status (high vs. low) will be presented by treatment group. OS function for each TMB subgroup will be estimated using the KM product limit method for each treatment arm and will be displayed graphically. A two-sided 95% CI for median OS in each arm will be computed via the log-log transformation method. Hazard ratios of OS and corresponding

two-sided 95% CI will be estimated using an unstratified Cox proportional hazard model, with treatment group as a single covariate.

OS HR comparing TMB high vs. TMB low subgroups among TMB-evaluable subjects from nivo + ipi arm will be displayed graphically as a function of TMB cutpoint. Cutoffs at 6, 8, 9, 10, 11, 13, 14, and 15 will be analyzed to visualize which TMB cutpoint gives the maximum difference between TMB high vs. low subgroups. Nivo mono arm will be analyzed similarly. Same plot will be generated for subjects randomized to placebo, to visualize potential prognostic effect of TMB on OS.

A Cox proportional hazards regression model will be fitted for OS with treatment (nivo + ipi vs. placebo), TMB status (high vs. low), and treatment by TMB status interaction. Although the study is not designed to have appropriate power to formally test the interaction of the model, an interaction test at significance level of 0.2 will warrant further exploration and the following statistics will be reported: interaction p-value, HR of Nivo + ipi vs. placebo and its associated 95% CI for each TMB subgroup, HR of TMB high vs. TMB low and its associated 95% CI for each treatment group. Idem for Nivo mono vs. placebo comparison.

Similar analysis will be run on PFS (per BICR assessment).

## 7.11 Outcomes Research Analyses

The outcome research analyses will be performed using all randomized subjects.

### 7.11.1 LCSS questionnaire

LCSS questionnaire completion rate, defined as the proportion of questionnaires actually received out of the expected number (i.e., the number of subjects still on treatment or in follow-up), will be calculated and summarized at each assessment point.

Baseline and change from baseline of the average symptom burden index score at each assessment point will be summarized using descriptive statistics (N, mean, median, SD, 25th and 75th percentiles) by treatment group, as randomized.

Kaplan-Meier plots for TTSD as measured by LCSS ASBI will be presented along with median TTSD and corresponding 95% CI. Hazard ratios and corresponding two-sided 95% CI will be estimated using unstratified Cox proportional hazard model, with treatment group as a single covariate. TTSD rates at fixed timepoints Week 6, 12 and 24 will be derived from the Kaplan Meier estimate and corresponding confidence interval will be derived based on Greenwood formula for variance derivation and on log-log transformation applied on the survivor function  $S(t)$ .

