Patient Reported Outcomes (PRO)	X	For on-treatment visits: Assessments (Lung Cancer Symptom Scale and EQ-5D) will be performed on treatment day prior to study treatment. Assessments will be performed at each cycle on Day 1 for the remainder of the first 6 months on study, then every 6 weeks thereafter for the remainder of the treatment period.
Health Resource Utilization	X	Except cycle 1. Note that concomitant medication collection will be included.
Clinical Drug Supplies		
Administer Blinded Study Drug	X	IVRS should be called within 1 day prior to blinded study drug administration to receive vial assignment. Note: The subject must receive the blinded study therapy within 3 business days of vial assignment. See Section 4.5.1 for minimum dosing intervals between Cycles. A call to IVRS is made for every dosing visit.

Table 5.1-4: Follow-Up Assessments for All Subjects (CA209451)

Procedure	Follow-Up ^a Visits 1 and 2	Survival Follow-Up ^b Visits	Notes
Safety Assessments			
Targeted Physical Examination	X		To assess for potential late emergent study drug related issues
Adverse Events Assessment	X	X	NSAEs and SAEs must be collected up to 100 days after blinded study drug discontinuation. SAEs that relate to any later protocol specified procedure must be collected. SAEs should be approved in TAO within 5 days from entry.
Review of Concomitant Medication	X	X	Collection of concomitant medications only for treatment-related AEs or SAEs until the medication is discontinued.
Extended Laboratory Tests	X		CBC with differential, uric acid, BUN or serum urea level, serum creatinine, sodium, potassium, calcium, magnesium, chloride, phosphorus, bicarbonate (optional), amylase or lipase, glucose, AST, ALT, total bilirubin, alkaline phosphatase, LDH
Thyroid Function Testing	X		TSH (reflex to free T3 and free T4 if abnormal result)
Pregnancy Test	X		Serum or urine
Efficacy Assessments			
Radiographic Tumor Assessment CT/MRI	See Note	See note	See Table 5.4-1 for CT/MRI
Outcomes Research Assessments			
Patient Reported Outcomes (PRO)	X	EQ-5D only	Both the Lung Cancer Symptom Scale and EQ-5D will be given in FU Visits 1 & 2. In Survival Visits, EQ-5D is collected every 3 months for the first year of the Follow-up Phase, then every 6 months thereafter. For Survival Visits these can be collected in person or via telephone contact.
Healthcare resource utilization	X		

Table 5.1-4: Follow-Up Assessments for All Subjects (CA209451)

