8.4.6 Outcomes Research Analyses

LCSS questionnaire complete rate, defined as the proportion of questionnaires actually received out of the expected number (ie, the number of subjects still on treatment and in follow-up), will be calculated and summarized at each assessment point.

Baseline and change from baseline of the average symptom burden index score at each assessment point will be summarized using descriptive statistics. Subject's overall health state on a visual analog scale (EQ-VAS) at each assessment time point and the difference from baseline will be summarized using descriptive statistics. Proportion of subjects reporting problems for the 5 EQ-5D dimensions at each assessment time point will be summarized by level of problem. Summary statistics will be calculated for the population preference-based health state utility score (EQ-5D Index).

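### The LCSS completion rate counts subjects who have no LCSS form due, so it understates compliance, increasingly so over time

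*SAP*

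**What the plan says.** SAP 7.11.1 defines the LCSS completion rate as "the proportion of questionnaires actually received out of the expected number (i.e., the number of subjects still on treatment or in follow-up", and the rate "will be calculated and summarized at each assessment point". Protocol 8.4.6 words the expected number as "the number of subjects still on treatment and in follow-up".

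The collection schedule is narrower. On treatment, LCSS is completed at the dosing visits of Cycles 1 and 2 (Table 5.1-2). From Cycle 3, Table 5.1-3 states: "Assessments will be performed at each cycle on Day 1 for the remainder of the first 6 months on study", and then every 6 weeks. After treatment, Table 5.1-4 states: "Both the Lung Cancer Symptom Scale and EQ-5D will be given in FU Visits 1 & 2". It schedules no LCSS after that: "In Survival Visits, EQ-5D is collected every 3 months for the first year of the Follow-up Phase", and every 6 months thereafter.

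Protocol 3.1.1.3 starts the Follow-up phase at the decision to stop blinded therapy. It places the survival visits inside that phase, after Follow-Up Visit 2.

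**The concern.** A completion rate should answer one question: of the forms that were due, how many came back? Here the denominator includes living subjects who have left treatment and have no LCSS due at the point being tabulated. They can only count as non-completers. The rate then mixes compliance with time on treatment.

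SAP 7.11.1 also reports change in the symptom burden index at each assessment point and time-to-symptom-deterioration rates at Weeks 6, 12 and 24. The completion rate is what a reader would use to judge how complete those data are. A rate that falls by construction could make well-collected data look badly incomplete, or unevenly incomplete between arms.

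**Working it through.** **The texts side by side.** Follow-Up Visit 1 (FU1) is 35 ± 7 days after last dose and Follow-Up Visit 2 (FU2) is 80 ± 7 days after FU1. FU2 therefore falls 28 + 73 = 101 days after last dose at the earliest, nominally at 35 + 80 = 115, and at 42 + 87 = 129 at the latest. Take Week 24 (Day 168 from first dose, a dosing visit):

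- Last dose at Day 21: FU2 is over by Day 21 + 129 = 150. If alive, the subject is in survival follow-up. No LCSS is due, but the subject is counted as expected.
- Last dose at Day 84: FU1 falls on Days 112–126 and FU2 on Days 185–213. No LCSS is due at Day 168, but the subject is counted.
- Last dose at Day 42: FU2 falls on Days 143–171, so a form may be due around Day 168.

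The first two cases establish the mismatch without a model.

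**The plan's own figures.** The documents give no completion rate and no time-on-treatment curve, so an illustration has to borrow the OS and PFS assumptions of SAP Section 5. As a check on those inputs, power = Φ(√d/2 × |ln HR| − 1.96):

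- PFS, d = 525, HR 0.74: 93.2% (stated about 93%).
- OS, d = 386, HR 0.72: 89.7% (stated about 90%).

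Constant hazards between the stated OS points give medians of 8.4 and 10.7 months against the stated 8.8 and 11.0, so the curves below are approximate.

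**Inputs.**
- Placebo OS 90%, 47%, 15% at 3, 9, 18 months. Hazards: −ln(0.90)/3 = 0.0351; ln(0.90/0.47)/6 = 0.1083; ln(0.47/0.15)/9 = 0.1269. Combination: the same to month 3, then × 0.68.
- PFS median 2 months in all arms; 12-month rate 5% (placebo), 15% (experimental). Hazard to month 2: ln 2/2 = 0.3466. After that: ln(0.50/0.05)/10 = 0.2303 and ln(0.50/0.15)/10 = 0.1204. The break at 2 months is an assumption.
- 1 month = 30.4375 days (SAP Section 8), so Week 24 = 5.52 and Week 48 = 11.04 months.
- Assumptions: on treatment = progression-free; every due form is returned.

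**Case 1: no follow-up visit form counts at the tabulated week.** Rate = PFS(t)/OS(t). For placebo at Week 24, OS = 0.90 × exp(−0.1083 × 2.52) = 0.685 and PFS = 0.50 × exp(−0.2303 × 3.52) = 0.222.

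| Point | Placebo | Combination |
|---|---|---|
| Week 6 | 0.620/0.953 = 65% | 0.620/0.953 = 65% |
| Week 12 | 0.420/0.908 = 46% | 0.456/0.908 = 50% |
| Week 24 | 0.222/0.685 = 32% | 0.327/0.748 = 44% |
| Week 48 | 0.062/0.363 = 17% | 0.168/0.485 = 35% |

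A Weibull PFS curve through the same two points gives 30% and 39% at Week 24.

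**Case 2: everyone within 115 days of last dose is credited with a form.** A simulation with post-progression mortality set to match OS at Week 24 splits the randomized subjects as follows:

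- Placebo: 22.3% on treatment, 23.8% in the FU1/FU2 phase, 22.5% in survival follow-up. Rate (22.3 + 23.8)/68.5 = 67%.
- Combination: 32.6%, 16.9% and 25.3%. Rate (32.6 + 16.9)/74.8 = 66%.

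**Case 3: an outer bound.** Credit everyone within 115 days (3.78 months) of last dose and assume none of them died: PFS(t − 115 days)/OS(t).

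- Week 24: 0.547/0.685 = 80% and 0.547/0.748 = 73%.
- Week 48: 0.149/0.363 = 41% and 0.265/0.485 = 55%. With the latest FU2 (129 days): 0.166/0.363 = 46% and 0.281/0.485 = 58%.

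**Sensitivity of Case 1 at Week 24.**
- If 10–30% of living subjects past a PFS event are still treated: 39–53% (placebo), 49–61% (combination).
- If 10–30% of combination subjects stop early for toxicity: 39% down to 31% in that arm. The gap closes at 1 − 0.325/0.438 = 26%.
- If survival follow-up is dropped from the denominator but FU1/FU2-phase subjects stay in it: 48% and 66%. Dropping survival follow-up alone therefore does not repair the rate.

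**The case against.** The strongest defence is that the governing idea is the expected number at each assessment point. LCSS assessment points are the dosing visits and FU1/FU2, and Table 5.1-4 labels those two visits separately from the survival visits. On that view the phrase means on-treatment subjects for treatment visits and FU1/FU2 subjects for those visits, and nothing is wrong. This is a possible intention. But the SAP does not say it, and Protocol 3.1.1.3 defines follow-up to include survival follow-up. If it was intended, one sentence is still needed to say so.

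Three stronger inferences are tempting, and the documents do not support them.

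- *Survival follow-up alone is the cause.* FU2 is at least 101 days after last dose, so no treated subject can be in survival follow-up at Week 12 (Day 84). The Week 12 shortfall comes entirely from subjects between last dose and FU2. At Week 24 about half of off-treatment placebo survivors (23.8/46.3) and 40% of combination survivors (16.9/42.2) are still in that phase.
- *Full compliance would be reported as one definite figure, such as 32% and 44% at Week 24.* That needs PFS to equal time on treatment and no FU1/FU2 form to count. Protocol 4.5.5 allows treatment beyond progression, and neither document assigns FU1/FU2 forms to calendar weeks.
- *The rule will create a false arm difference.* It can, if time on treatment differs. It is nearly absent in Case 2 and could vanish with early toxicity stopping in the combination arm.

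The *and*/*or* difference is minor. Read strictly, the protocol's *and* would describe almost nobody, since one phase ends as the other begins. The ordinary reading is both groups together, which matches the SAP.

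It is also fair that SAP 7.11.1 already reports N at each point, so attrition is visible, and that no test or threshold uses the completion rate.

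**Conclusion.** The point holds on the text: the stated denominator includes subjects who owe no LCSS form, both in survival follow-up and between FU1 and FU2, so the rate falls over time under perfect compliance. Its size is illustrative. With PFS as a proxy for time on treatment, full compliance would be reported as roughly 30–67% at Week 24, depending mainly on how FU1/FU2 forms are counted; the outer bound that ignores deaths is 80% and 73%. At Week 48 it would be at most about 41% (placebo) and 55% (combination) with FU2 at its nominal time. Treatment beyond progression would raise these figures and early stopping for toxicity would lower them. An arm difference is possible, not established. The consequence is confined to a descriptive patient-reported outcome table. OS, PFS, alpha and power are untouched.

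**What to change.** In SAP 7.11.1, define the denominator at each assessment point as subjects with an LCSS due at that point under Protocol Tables 5.1-2 to 5.1-4:

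- on-treatment points: subjects alive and on treatment;
- FU1 and FU2: subjects reaching that visit, tabulated as their own assessment points;
- survival follow-up: excluded.

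Align Protocol 8.4.6 to the same wording. With this denominator, full return gives 100% in every arm by construction. At Week 24 the modelled expected number drops from all survivors (68.5% and 74.8% of those randomized) to those on treatment (22.2% and 32.7%). A separate column showing forms completed out of all randomized subjects would keep attrition in view; that is optional.

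The cost is one SAP sentence, a matching phrase in the protocol and a change to the denominator program. No new data are needed.

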## 2.2 Treatment Assignment

Subjects are enrolled using the Interactive Voice Response System (IVRS) to obtain a subject ID. Subjects who have signed informed consent and met all eligibility criteria will be ready to be randomized through the IVRS, upon confirmation of receipt of required tissue sample by the central lab. The following information is required for subject randomization:

- Subject number
- Date of birth
- Submission of tumor tissue sample to central lab
- ECOG Performance Status: 0 vs. 1
- Sex: Male vs. Female
- Prophylactic Cranial Irradiation (PCI) following chemotherapy: Yes vs. No

The IVRS will randomly assign the subject in a 1:1:1 ratio to either Arm A (nivolumab), Arm B (nivolumab/ ipilimumab), or Arm C (placebo), stratified by the following factors:

- ECOG Performance Status: 0 vs. 1
- Sex: Male vs. Female
- Prophylactic Cranial Irradiation (PCI) following chemotherapy: Yes vs. No

The randomization will be carried out via permuted blocks within each stratum.

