## 5 SAMPLE SIZE AND POWER

Per original protocol, approximately 810 subjects were to be randomized to three treatment arms in a 1:1:1 ratio.

The primary objective is to compare OS of nivolumab in combination with ipilimumab versus placebo. The analysis of primary endpoint of OS will be conducted when at least 386 deaths have been observed pooled across the two treatment groups. With 386 events available for comparison of OS in nivolumab in combination with ipilimumab vs placebo, power of the log-rank test is approximately 90% to detect a hazard ratio (HR) of 0.72 with a type I error of 0.05 (two-sided). The critical hazard ratio for determining whether nivolumab in combination with ipilimumab is superior to placebo is 0.82.

Power calculations were performed using EAST® Software (version 6.4.1). Results were generated by 10000 simulations. Model assumptions were as follows:

Survival function for placebo arm was modeled using a four hazard pieces: OS rates at 3, 9, 18 and 26 months were assumed to be 90%, 47%, 15% and 9%, respectively, based on published survival curve for placebo maintenance in extensive-stage disease SCLC, adjusted for induction phase.

For nivolumab in combination with ipilimumab, a delayed effect versus placebo with a hazard ratio (HR) of 1 for the first 3 months and an HR of 0.68 thereafter was assumed, resulting into overall HR (experim over placebo) of 0.72 at time of the OS analysis, as determined from the 10000 simulations.

Median OS derived from the survival functions were 8.8 months and 11.0 months for the placebo and experimental treatment groups, respectively. Accrual information used in the simulations had the same pattern as the actual data at time of the protocol amendment (832 subjects were accrued in 28 months and randomized to the three treatment groups). A 5% probability of dropout by month 6 was taken into account. Given the observed accrual and dropout and survival assumptions it is expected that the duration of the study from start of randomization to analysis of OS will be approximately 35 months (28 months of accrual + 7 months of follow-up, providing an average follow up of 9 months).

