### 7.1 General Methods

Unless otherwise noted, the bulleted titles in the following subsections describe tabulations of discrete variables, by the frequency and proportion of subjects falling into each category, grouped by treatment (with total). Percentages given in these tables will be rounded and, therefore, may not always sum to 100%. Continuous variables will be summarized by treatment group (with total) using the mean, standard deviation, median, minimum and maximum values.

Time to event distribution (i.e. progression free survival, overall survival and duration of response) will be estimated using Kaplan Meier techniques.

Median survival time along with 95% CI will be constructed based on a log-log transformed CI for the survivor function  $S(t)$ . Rates at fixed timepoints (e.g. OS at 6 months) will be derived from the Kaplan Meier estimate and corresponding confidence interval will be derived based on Greenwood formula for variance derivation and on log-log transformation applied on the survivor function  $S(t)$ .

Unless otherwise specified, the stratified log-rank test will be performed to test the comparison between time to event distributions (OS and PFS). Stratification factors will be ECOG PS (0, 1), sex (male, female) and Prophylactic Cranial Irradiation (PCI) following chemotherapy (yes, no), as entered into the IVRS.

Unless otherwise specified, the stratified hazard ratio between 2 treatment groups along with CI will be obtained by fitting a stratified Cox model with the treatment group variable as unique covariate. Stratification factors will be same as above.

Confidence intervals for binomial proportions will be derived using the Clopper-Pearson method. The difference in rates between the two treatment arms along with their two-sided

95% CI will be estimated using the following Cochran-Mantel-Haenszel (CMH) method of weighting, adjusting for the stratification factors:

$$\hat{\theta} = \frac{\sum_i w_i \hat{\theta}_i}{\sum_i w_i} \sim N \left[ \theta, \frac{\sum_i w_i^2 \left[ \frac{p_{ix}(1-p_{ix})}{n_{ix}-1} + \frac{p_{iy}(1-p_{iy})}{n_{iy}-1} \right]}{\left( \sum_i w_i \right)^2} \right]$$

where  $\hat{\theta} = p_{ix} - p_{iy}$  is the rate difference of the *i*th stratum,  $w_i = \frac{n_{ix}n_{iy}}{n_{ix} + n_{iy}}$ , and  $n_{ix}$  and  $n_{iy}$  are the number of subjects randomized to treatments x and y, respectively, in the *i*th stratum.

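### The time-to-symptom-deterioration hazard ratio is given only from an unstratified Cox model, although randomization and the SAP's OS and PFS hazard ratios are stratified: a small, exploratory point with a one-line fix

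*SAP*

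**What the plan says.** - **TTSD model.** SAP 7.11.1 plans Kaplan-Meier plots, medians, rates at Weeks 6, 12 and 24, and hazard ratios with 95% CIs "estimated using unstratified Cox proportional hazard model, with treatment group as a single covariate". SAP 7.11 sets the population as all randomized subjects. No stratified TTSD hazard ratio is planned beside it.
- **Default.** SAP 7.1: "Unless otherwise specified, the stratified hazard ratio between 2 treatment groups along with CI will be obtained by fitting a stratified Cox model". The factors are set out in the same section: "Stratification factors will be ECOG PS (0, 1), sex (male, female) and Prophylactic Cranial Irradiation (PCI) following chemotherapy (yes, no), as entered into the IVRS".
- **Randomization.** SAP 2.2: "The randomization will be carried out via permuted blocks within each stratum", with the same three factors.
- **Other hazard ratios in all randomized subjects.** OS (SAP 7.5.1), BICR PFS (7.5.2) and investigator PFS (7.5.2.1) are stratified. The unstratified OS comparison is a sensitivity analysis (7.5.1.1).
- **Other unstratified hazard ratios.** OS and PFS subgroups (7.5.1.2, 7.5.2.2) and TMB subsets (7.10.1.3).
- **Status.** Protocol 8.4.7 treats the patient-reported outcome analyses as exploratory. The testing hierarchy in SAP 7.5.3 covers OS and PFS only, and 7.11.1 plans no TTSD p-value. The SAP document history shows that the TTSD hazard ratio was added in version 2.0.

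**The concern.** In the readable text, TTSD is the only between-arm comparison of all randomized subjects whose hazard ratio with treatment as sole covariate is planned solely without strata. Sparse data could justify dropping strata within a subgroup or a TMB subset, but they are not an evident reason here.

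Two consequences follow if the factors predict symptom deterioration. First, a non-null hazard ratio from a model that omits them lies nearer 1 than the within-stratum hazard ratio, which is the kind reported for OS and PFS. Second, a model that ignores stratified randomization overstates the sampling variation of its own estimate, so its confidence interval is too wide. SAP 7.5.1.3 and 7.5.2.3 list all three factors as potentially prognostic for OS and PFS. It is reasonable, though not shown in the documents, to expect the same of ECOG PS for symptoms.

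At stake is how the TTSD estimate and interval read in the study report. No alpha and no confirmatory conclusion depend on them.

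**Working it through.** **1. The plan's own figures.** The documents give no effect size, event count or power for TTSD. The nearest planning figures are for OS in SAP 5: the analysis is "conducted when at least 386 deaths have been observed pooled across the two treatment groups", with power "approximately 90% to detect a hazard ratio (HR) of 0.72 with a type I error of 0.05 (two-sided").
- Power = Φ(½·√386·|ln 0.72| − 1.96) = Φ(9.823 × 0.3285 − 1.96) = Φ(1.267) = 0.897, against about 90% stated.
- Events for 90% power = 4(1.96 + 1.2816)² / (ln 0.72)² = 390, against 386.
- Critical HR = exp(−2 × 1.96/√386) = 0.819, against 0.82.

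The OS figures reproduce. They say nothing about TTSD. The 0.72 is borrowed below only as an illustrative true effect.

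**2. Inputs for the TTSD check.**
- From the documents: 810/3 = 270 per arm, so 540 per pairwise comparison; 2 × 2 × 2 = 8 strata, on average 540/8 = 67.5 subjects each.
- Assumed: exponential times, factor prevalences, event rate, censoring, and the prognostic hazard ratio of each factor. The large-sample runs used prevalences 0.60/0.37/0.55 and a median of 4 months.

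**3. Large-sample shift, true within-stratum HR 0.72.** 600,000 simulated subjects per setting, with about 37% to 100% having an event.

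| HR of each factor | Unstratified minus stratified HR | Ratio of log HRs |
|---|---|---|
| 1.2/1.2/1.2 | 0.002 to 0.006 | 0.976 to 0.990 |
| 1.3/1.3/1.3 | 0.003 to 0.011 | 0.956 to 0.988 |
| 1.5/1.3/1.5 | 0.007 to 0.017 | 0.927 to 0.971 |
| 2.0/1.5/2.0 | 0.020 to 0.044 | 0.817 to 0.918 |

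With a true HR of 1.0 there is no shift beyond simulation noise.

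**4. Trial-size shift.** n = 540, permuted blocks within the 8 strata, true HR 0.72. Two separate simulations of this design:

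| HR of each factor | Unstratified vs stratified, run 1 | Run 2 |
|---|---|---|
| 1.5/1.3/1.5 (moderate) | 0.731 vs 0.721 | 0.729 vs 0.719 |
| 2.0/1.5/1.8 (strong) | 0.739 vs 0.717 | 0.743 vs 0.720 |

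On the log scale in run 1, the moderate shift is 0.3271 − 0.3133 = 0.014 and the strong shift is 0.3327 − 0.3025 = 0.030. Against a standard error of about 0.12 these are roughly a tenth and a quarter of one standard error.

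**5. Interval width near the null, same design, true HR 1.**
- Strong effects, run 1: the unstratified model SE averages 0.121 against an empirical SD of 0.115; 0.121/0.115 = 1.05, so the CI is about 5% too wide. Run 2 gives 0.120 against 0.114, and a nominal 5% test would reject 4.0% of the time.
- The stratified fit is calibrated: 0.123 against 0.122 in run 2, rejection 5.3%.
- Moderate effects: excess width about 2%, rejection 4.9% for both fits.

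Stratifying does not shorten the interval (0.123 against 0.120). It makes the stated width match the sampling variation of the estimate.

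**6. Price of stratifying.** With no prognostic effect, n = 540 and about 321 events, the SE is 0.1165 stratified against 0.1130 unstratified; 0.1165/0.1130 = 1.03. The blocked run gave about 2%. Power, used only as a measure of precision, is 81.5% vs 83.1% in the first of these and 71.0% vs 73.1% in the blocked run, lower for the stratified fit both times. With prognostic strata the order reverses in the blocked run: stratified 72.5% vs 71.6% (moderate) and 71.7% vs 66.0% (strong).

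**The case against.** The strongest reply is that the SAP made a permitted choice. The default in 7.1 gives way where another method is specified, and 7.11.1 specifies one. A reader might infer that the SAP contradicts itself; it does not. That part of the reply stands in full.

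Next, the unstratified hazard ratio is a marginal quantity that matches the unstratified Kaplan-Meier curves, medians and rates shown with it. A reader might infer that the planned estimate is biased. The gap in steps 3 and 4 is better described as non-collapsibility, a difference between two estimands, and it needs both prognostic strata and a real treatment effect. The documents give evidence of neither for TTSD. This also stands, but it does not answer step 5: the interval around the marginal estimate is still too wide when prognostic strata were balanced by design.

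A reader might also infer that leaving out the strata brings no benefit. Step 6 contradicts that: if the strata do not matter, the unstratified fit is slightly more precise.

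Power is a weak argument here because no TTSD test is planned. Comparability with OS and PFS is also limited, since these are different endpoints; the narrower point that their hazard ratios would be conditional on strata and the TTSD one would not remains true. Finally, the TTSD definition in SAP 4.3.3 is blacked out, so its event rate and censoring cannot be checked. The readable text gives no reason for the choice, but one cannot be ruled out.

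**Conclusion.** The point holds as a minor one. The TTSD hazard ratio departs from the stratified randomization and from the SAP's handling of OS and PFS, without a visible reason and without a stratified estimate beside it. Under assumed strata effects and a true HR of 0.72, the attenuation relative to the within-stratum hazard ratio is about 0.01 (moderate, to about 0.73) or about 0.02 (strong, to about 0.74). The confidence interval near the null is about 2% or 5% too wide respectively. At a hazard ratio of 1, or with non-prognostic strata, the estimate does not shift.

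All these sizes rest on assumed prevalences, event rates and prognostic effects. The documents support no claim of a broken SAP rule, of a biased trial result, or of any effect on the OS or PFS conclusions. This is a low-severity improvement.

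**What to change.** In SAP 7.11.1, specify the TTSD Cox model as stratified by ECOG PS, sex and PCI (IVRS source), as in SAP 7.1, and report the unstratified hazard ratio as supportive. If the unstratified model was chosen on purpose, one sentence giving the reason would be the minimum. Either edit should be made before treatment codes are released for analysis.

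The change is one line in the SAP and a strata statement in the program. It needs no new data, leaves the Kaplan-Meier output as planned and touches no alpha. The downside is a standard error about 2–3% larger if the three factors do not predict symptom deterioration.
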